8.6.2 Statistical Methods for Safety Analyses

Safety and tolerability will be assessed by clinical review of all relevant parameters including adverse events. Comparisons will be made between the V114 lots and Prevnar 13™ following each dose, and across all doses as outlined below.

The analysis of safety results will follow a tiered approach. The tiers differ with respect to the analyses that will be performed. For Tier 1 safety endpoints (those adverse events specifically prompted on the VRC), point estimates, risk differences with 95% CIs and corresponding p-values will be provided. Tier 2 parameters will be assessed via point estimates and risk differences with 95% CIs. These analyses will be performed using the Miettinen and Nurminen method. Only point estimates by group will be provided for Tier 3 safety parameters.

Tier 1 safety endpoints include solicited injection-site adverse events (redness, swelling, hard lump, and pain/tenderness) during Day 1 to Day 14 postvaccination, and solicited systemic adverse events (irritability, drowsiness, hives/welts, appetite loss) during Day 1 to Day 14 postvaccination.

Adverse events (specific terms as well as system organ class terms) will be classified as belonging to "Tier 2" or "Tier 3", based on the number of events observed. Membership in Tier 2 requires that at least 4 subjects in any vaccination group exhibit the event; all other adverse events will belong to Tier 3. In this trial, temperatures collected from Day 1 through Day 7 will be treated as Tier 2 events and will be summarized.

The threshold of at least 4 events was chosen because the 95% CI for the between-group difference in percent incidence will always include zero when vaccination groups of equal size each have less than 4 events and thus would add little to the interpretation of potentially meaningful differences. Because many 95% CIs may be provided without adjustment for multiplicity, the CIs should be regarded as a helpful descriptive measure to be used in review, not a formal method for assessing the statistical significance of the between-group differences in adverse events.

For this protocol, the broad clinical adverse event categories consisting of the percentage of subjects with any adverse event, a vaccine-related adverse event, with a serious adverse event, with an adverse event which is both vaccine-related and serious, and who died or discontinued due to an adverse event will be considered Tier 2 endpoints.

Table 4 Analysis Strategy for Safety Parameters

Safety Tier	Safety Endpoint [†]	p-Value	95% CI for Comparison	Descriptive Statistics
Tier 1	Injection-site redness (Days 1 to 14)	X	X	X
	Injection-site swelling (Days 1 to 14)	X	X	X
	Injection-site pain or tenderness (Days 1 to 14)	X	X	X
	Injection-site hard lump (Days 1 to 14)	X	X	X
	Irritability (Days 1 to 14)	X	X	X
	Drowsiness (Days 1 to 14)	X	X	X
	Hives/welts (Days 1 to 14)	X	X	X
	Appetite loss(Days 1 to 14)	X	X	X
Tier 2	Any AE		X	X
	Any Serious AE		X	X
	Any Vaccine-Related AE		X	X
	Any Serious and Vaccine-Related AE		X	X
	Discontinuation due to AE		X	X
	Specific AEs or SOCs [‡] (incidence ≥ 4 of subjects in one of the vaccination groups)		X	X
	Body temperature (Day 1 to 7)		X	X
Tier 3	Specific AEs or SOCs [‡] (incidence < 4 of subjects in all vaccination groups)			X

[†] Adverse event (AE) references refer to both Clinical and Laboratory AEs.

[‡] Includes only those endpoints not pre-specified as Tier 1 or not already pre-specified as Tier-2 endpoints.

SOC=System Organ Class

X= results will be provided.

8.6.3 Summaries of Demographics and Baseline Characteristics

The comparability of the vaccination groups for each relevant demographic and baseline characteristic will be assessed by the use of summary tables. No statistical hypothesis tests will be performed on these characteristics. The number and percentage of subjects randomized and vaccinated, and the reasons for discontinuation (including subjects discontinued for meeting the rescue criterion), will be displayed by group. Demographic variables (e.g., age), prior and concomitant therapies and vaccines will be summarized by group.

8.7 Interim Analyses

An interim analysis of the immunogenicity will be performed in this trial when ~100% PD3 safety follow-up completed and ~100% PD3 immunogenicity results (IgG responses) are available. Group summaries of the IgG results will be reviewed; however, the project team will not be unblinded at the subject level. The Sponsor's trial team will use the results to make scientific decisions regarding future studies. The conduct of this trial will not be altered by the interim analysis. The Haybittle-Peto rule using 1-sided significance level of $\alpha = 0.0005$ will be utilized to account for the interim analysis. The final analysis will still be evaluated at a 1-sided significance level of $\alpha = 0.025$.

The endpoints, timing, and purpose of the interim analysis are summarized in Table 5.

[figure not shown]
Table 5 Summary of Interim Analysis Strategy

Key Endpoints for Interim Analysis	Timing of Interim Analysis	Purpose of Interim Analysis

 Proportion of subjects with PD3 IgG ≥ 0.35 μg/mL for all 15 serotypes in V114 The PD3 IgG GMCs for all 15 serotypes included in V114 PD3 percentage of subjects with any AE, a vaccine related AE, a serious AE, and an AE which is both vaccine-related and serious, and who died or discontinued due to an AE. 	
$\sim 100\%$ PD3 safety follow-up completed and $\sim 100\%$ PD3 immunogenicity results (IgG responses) are available
	Inform scientific decisions for future studies

8.8 Multiplicity

Non-inferiority tests will be conducted for the 13 shared serotypes between V114 and Prevnar 13TM. The overall success for each of the V114 lots requires demonstrating non-inferior to Prevnar 13TM for each of the 13 serotypes. This approach controls the overall type I error within each lot, therefore no multiplicity adjustment will be required within each lot.

The type I error for the primary immunogenicity analysis will be controlled at the one-sided significant level of 0.025 by testing V114-1 and V114-2 simultaneously using a Hochberg approach, which is summarized in [Figure 2](#).

The success of either V114-1 or V114-2 requires demonstrating non-inferior to Prevnar 13TM for each of the 13 shared serotypes (1, 3, 4, 5, 6A, 6B, 7F, 9V, 14, 18C, 19F, 19A, and 23F).

Figure 2 Diagram of the Multiplicity Adjustment

Both lots will first be tested using a 1-sided alpha of 0.025 respectively. If all tests for both lots are significant ($p\text{-value} < 0.025$) or at least one test for both lots is non-significant ($p\text{-value} \geq 0.025$), testing is complete. However, if one lot is successful at the 1-sided alpha of 0.025 and the other is not, the successful lot will be re-tested at a more stringent 1-sided alpha of 0.0125 (0.025/2). The level of the confidence interval will align with the type I error during the re-testing procedure, i.e., the 97.5% CI will be provided if only one of the two lots succeeds. Testing in this manner controls the type I error for the primary immunogenicity analysis at the 1-tailed $\alpha=0.025$.

The Haybittle-Peto rule using 1-sided significance level of $\alpha =0.0005$ will be utilized to account for the interim analysis. The final analysis will still be evaluated at a 1-sided significance level of $\alpha =0.025$ as described in Section 8.7.

No multiplicity adjustments will be made for the safety comparisons.

8.9 Sample Size and Power Calculations

8.9.1 Immunogenicity Analyses

Approximately 1050 subjects will be enrolled, with approximately 350 subjects in each of the three vaccination groups. For the primary immunogenicity hypotheses, the power is simulated based on the Hochberg approach. There is $>90\%$ power to declare non-inferiority to Prevnar 13TM for the 13 common serotypes between V114 and Prevnar 13TM and superiority for the two serotypes unique to V114 for at least one of the V114 lots based on the proportion of subjects meeting the serotype-specific IgG ≥ 0.35 $\mu\text{g/mL}$. This power assumes an 85% evaluability rate (~ 298 subjects per group), a non-inferiority margin of -0.15 for the difference (V114 – Prevnar 13TM), and a serotype-specific true percentage of the response rate based on the group level results from the V114-003 CSR, the V114-004 interim analysis and the knowledge of the V114 formulation that will be used in this trial. Based on this knowledge, it was conservatively assumed that the true response rates of V114 will be 0.05 lower than that of Prevnar 13TM for serotypes 6A, 6B, and 19A, 0.20 higher for serotype 3, and the same for the remaining serotypes. The assumption of the true percentage for each serotype can be found in [Table 6](#).

Note that the overall power is sensitive to the assumed response rate of V114 for the serotypes which are assumed to have lower response rates (6A, 6B, and 19A). For example, if the V114 response rate for 6B is decreased from 0.82 to 0.80 (0.07 lower than that of Prevnar 13TM), the power will be $\sim 80\%$.

Further details are provided in the sSAP.

Table 6

PCI

8.9.2 Safety Analyses

For safety comparisons, all subjects are expected to be evaluable. If no serious adverse event is observed among the 350 subjects in each vaccination group, this trial provides 97.5% confidence that the true serious adverse event rate is <1.05% (1 out of every 95 subjects).

The probability of observing at least one serious adverse event in this trial depends on the number of subjects enrolled and the incidence rate of serious adverse events in the general population. If the incidence rate of a serious adverse event is 1 of every 217 recipients of the vaccine (0.46%), then there is an 80% chance of observing at least one such serious adverse event among 350 subjects in the vaccine group. If the incidence rate is 1 of every 505 recipients (0.2%), there is a 50% chance of observing at least one serious adverse event.

For safety comparisons, risk differences between any 2 vaccination groups that could be detected with an 80% probability are summarized in [Table 7](#) for a variety of hypothetical true incidence rates. These calculations assume there are 350 subjects for safety in both groups and are based on a 2-sided significance level of $\alpha = 0.05$. No multiplicity adjustments were made in these calculations.

Table 7 Differences in Incidence of Adverse event Rates between the Two Vaccination Groups That Can be Detected With an ~80% Probability and a Two-Sided Significance Level of 0.05

True Incidence Rate of Adverse events in V114 (%) N=350	True Incidence Rate of Adverse events in Prevnar 13™ (%) N=350	Detectable Percentage Point Difference in Incidence Rates of Adverse events
2.5	0.1	2.4
6.2	2.0	4.2
10.7	5.0	5.7
17.3	10.0	7.3
23.3	15.0	8.3
29.1	20.0	9.1
40.1	30.0	10.1

NOTE: The incidence rates for each vaccination group are hypothetical.

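### Table 7, first row (2.5% vs 0.1%): the ~80% power label holds only under a large-sample approximation; under the planned Miettinen-Nurminen method power is about 90%, and ~80% is reached at a difference of about 1.9 points

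*Combined protocol and SAP*

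**What the plan says.** Section 8.9.2 introduces Table 7 by saying that "risk differences between any 2 vaccination groups that could be detected with an 80% probability are summarized in" it. The table title repeats the claim as differences that "Can be Detected With an ~80% Probability and a Two-Sided Significance Level of 0.05". The stated conditions are:

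- **Group size:** "These calculations assume there are 350 subjects for safety in both groups".
- **Evaluability:** "For safety comparisons, all subjects are expected to be evaluable".
- **Multiplicity:** "No multiplicity adjustments were made in these calculations".

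The first row pairs a V114 rate of 2.5% with a Prevnar 13 rate of 0.1% and a detectable difference of 2.4 points. A note says that the rates are hypothetical. The section names no power formula.

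For the analysis, section 8.6.2 says of the Tier 1 and Tier 2 comparisons: "These analyses will be performed using the Miettinen and Nurminen method". It names no other method for comparing adverse event rates between groups. The same section justifies its 4-event threshold for Tier 2 by saying that the 95% interval for the difference "will always include zero when vaccination groups of equal size each have less than 4 events".

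**The concern.** A reader will take a difference that can be detected to mean one that the planned analysis would detect. At a control rate of 0.1%, 350 infants are expected to yield 350 × 0.001 = 0.35 events, and the V114 arm 350 × 0.025 = 8.75. A normal approximation to the difference is doubtful at such counts, so the ~80% label on this row needs to be checked against the exact behaviour of the planned test.

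This is the only row of Table 7 with a control rate near zero. It is therefore the plan's one statement about how large an excess of an otherwise very rare event the trial could detect, and describing the safety profile is the first primary objective. If the label is wrong, the trial's sensitivity to a rare-event excess is misdescribed.

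**Working it through.** **Inputs.** From section 8.9.2 and Table 7: n = 350 per group, two-sided α = 0.05 (critical value 1.960), p1 = 0.025, p2 = 0.001, all subjects evaluable, no multiplicity adjustment. From section 8.6.2: the Miettinen-Nurminen method.

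**Step 1: reproduce the stated figure.** The standard formula, pooled variance under the null and unpooled under the alternative, is

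power = Φ{ [(p1 − p2)√n − 1.960·√(2p̄(1 − p̄))] / √(p1(1 − p1) + p2(1 − p2)) }, with p̄ = (p1 + p2)/2 = 0.013.

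- (p1 − p2)√n = 0.024 × 18.708 = 0.4490
- 1.960 × √(2 × 0.013 × 0.987) = 1.960 × 0.16019 = 0.3140
- √(0.025 × 0.975 + 0.001 × 0.999) = 0.15929
- (0.4490 − 0.3140)/0.15929 = 0.848, and Φ(0.848) = 80.2%

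Solved for 80% power, the formula gives a difference of 2.39 points. Applied to all seven rows it gives 79.8% to 80.4%. Table 7 is consistent with this formula throughout.

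**Step 2: find the rejection region of the planned test.** At a null difference of zero the Miettinen-Nurminen statistic is

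z = (x1 − x2)/n ÷ √[ p̃(1 − p̃)·(2/n)·2n/(2n − 1) ], with p̃ = (x1 + x2)/(2n), rejecting when |z| ≥ 1.960.

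For 4 vs 0 events z = 2.004, which rejects. For 3 vs 0 events z = 1.735, which does not. This agrees with the 4-event threshold in section 8.6.2. With 1, 2 and 3 control events, rejection needs at least 7, 9 and 11 V114 events.

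**Step 3: exact power at 2.5% vs 0.1%.** The sum runs over control counts from Binomial(350, 0.001) and V114 counts from Binomial(350, 0.025):

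| Control events | Probability | V114 events needed | Probability of reaching them | Product |
|---|---|---|---|---|
| 0 | 0.7046 | ≥ 4 | 0.9760 | 0.6876 |
| 1 | 0.2468 | ≥ 7 | 0.7729 | 0.1908 |
| 2 | 0.0431 | ≥ 9 | 0.5123 | 0.0221 |
| 3 | 0.0050 | ≥ 11 | 0.2630 | 0.0013 |
| 4 or more | < 0.001 | ≥ 12 | – | about 0.0001 |

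The total is 0.902, or 90.2%. Most of the power comes from the 70% chance of no control event at all, when 4 V114 events are enough.

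**Step 4: the other rows, same enumeration.**

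| Row | Normal approximation | Enumerated |
|---|---|---|
| 2.5 vs 0.1 | 80.2% | 90.2% |
| 6.2 vs 2.0 | 80.1% | 82.5% |
| 10.7 vs 5.0 | 80.2% | 81.2% |
| 17.3 vs 10.0 | 80.4% | 80.8% |
| 23.3 vs 15.0 | 79.8% | 80.0% |
| 29.1 vs 20.0 | 80.0% | 80.2% |
| 40.1 vs 30.0 | 80.1% | 80.3% |

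**Step 5: where enumerated power is 80% at a 0.1% control rate.** Power is 79.7% at 2.00%, 80.2% at 2.02%, 81.0% at 2.05% and 82.3% at 2.10%. The crossing is at a V114 rate of about 2.01%, a difference of 1.91 points. The printed 2.4 points exceeds this by about a quarter (2.4/1.91 = 1.26).

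**Step 6: rounding of the printed rates.** With the control rate between 0.05% and 0.149% and the V114 rate between 2.45% and 2.549%, enumerated power runs from about 85% to about 94%.

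**The case against.** The strongest reply is that Table 7 is correctly computed. One conventional formula returns every row at ~80%. Section 8.9.2 never says that the table is exact power, and section 8.6.2 names Miettinen-Nurminen for analysing the data, not for planning. The normal approximation applied to the Miettinen-Nurminen statistic itself also gives about 80.1%. The answer for this row depends on the method: Fisher's exact test has 79.1% power, and an arcsine approximation gives 92.0%.

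Much of that stands. A reader might infer that the sponsor made an arithmetic error, and the reproduction in step 1 rules this out. What does not stand is the use of the approximation at this control rate: with 0.35 expected events it misses the planned test's actual power by about 10 points. Fisher's test lands near 80%, but it is not the planned method.

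It is also fair to say that nothing turns on the row. Its rates are hypothetical, it understates power, and section 8.6.2 treats the safety intervals as descriptive. A reader might infer that the trial is wrongly sized for safety or that a safety conclusion is at risk. The documents do not support this: the enrolment figure is tied to the immunogenicity power in section 8.9.1, and no rule refers to Table 7.

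**Conclusion.** The point holds as a limited correction. The first row's ~80% is a large-sample figure. The planned Miettinen-Nurminen comparison has about 90% power there (about 85% to 94% allowing for rounding) and reaches ~80% at about 2.0% vs 0.1%, a difference of about 1.9 points and not 2.4. The material gap is confined to this row: the second is 2.5 points above 80%, and the rest are within about 1 point.

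The error is on the safe side, because the trial is more sensitive to a rare-event excess than the table says. The result rests on independent binomial counts with 350 infants per group, a two-sided 0.05 level without adjustment, and detection read as rejection by the method in section 8.6.2. That the table was built with the normal approximation is inferred from its reproducing all seven rows; the documents do not state it.

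**What to change.** Either replace the first row with about 2.0% vs 0.1% (difference about 1.9 points), or keep 2.5% vs 0.1% and state its power as ~90%. In both cases add a footnote saying that the lowest-rate row comes from exact enumeration of the planned Miettinen-Nurminen test and the remaining rows from the normal approximation, once the sponsor has confirmed that formula. The cost is one table row and one footnote, with no change to sample size, analysis or conduct.

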8.10 Subgroup Analyses and Effect of Baseline Factors

The GMC responses as measured by Pn ECL to all 15 serotypes contained in V114 will be summarized by vaccination group in each country subgroup, in order to assess potential differences by this factor.

8.11 Extent of Exposure

The number of subjects vaccinated will be summarized by vaccination group.

9.0 LABELING, PACKAGING, STORAGE AND RETURN OF CLINICAL SUPPLIES

9.1 Investigational Product

The investigator shall take responsibility for and shall take all steps to maintain appropriate records and ensure appropriate supply, storage, handling, distribution and usage of investigational product in accordance with the protocol and any applicable laws and regulations.

Clinical Supplies will be provided by the Sponsor as summarized in [Table 8](#).

Table 8 Product Descriptions

Product Name & Potency	Dosage Form	Source/Additional Information
V114 Lot 1	0.5 mL dose sterile suspension for I.M. injection	Provided centrally by the Sponsor
V114 Lot 2	0.5 mL dose sterile suspension for I.M. injection	Provided centrally by the Sponsor
Prevnar 13™	0.5 mL dose sterile suspension for I.M. injection	Provided centrally by the Sponsor

9.2 Packaging and Labeling Information

Clinical supplies will be affixed with a clinical label in accordance with regulatory requirements.

Sites will receive open label single dose syringe kits. Each kit will contain 1 syringe.

9.3 Clinical Supplies Disclosure

This trial is blinded but supplies are provided open label; therefore, an unblinded pharmacist or qualified trial site personnel will be used to blind supplies. Vaccine identity (name, strength or potency) is included in the label text; random code/disclosure envelopes or lists are not provided.

The emergency unblinding call center will use the treatment/randomization schedule for the trial to unblind subjects and to unmask vaccine identity. In the event that the emergency unblinding call center is not available for a given site in this trial, the central electronic treatment allocation/randomization system (IVRS/IWRS) should be used in order to unblind subjects and to unmask treatment/vaccine identity. The Sponsor will not provide random code/disclosure envelopes or lists with the clinical supplies.

Vaccine identification information is to be unmasked ONLY if necessary for the welfare of the subject. Every effort should be made not to unblind the subject unless necessary.

In the event that unblinding has occurred, the circumstances around the unblinding (e.g., date, reason and person performing the unblinding) must be documented promptly, and the Sponsor Clinical Director notified as soon as possible. Only the principal investigator or delegate and the respective subject's code should be unblinded. Trial site personnel and Sponsor personnel directly associated with the conduct of the trial should not be unblinded to treatment assignment. Subjects whose treatment assignment has been unblinded (by the investigator, Merck subsidiary, or through the emergency unblinding call center) must be discontinued from study drug, but should continue to be monitored in the trial.

9.4 Storage and Handling Requirements

Clinical supplies must be stored in a secure, limited-access location under the storage conditions specified on the label.

Receipt and dispensing of trial medication must be recorded by an authorized person at the trial site.

Clinical supplies may not be used for any purpose other than that stated in the protocol.

9.5 Discard/Destruction/Returns and Reconciliation

The investigator is responsible for keeping accurate records of the clinical supplies received from the Sponsor or designee, the amount dispensed to and returned by the subjects and the amount remaining at the conclusion of the trial. For all trial sites, the local country Sponsor personnel or designee will provide appropriate documentation that must be completed for drug accountability and return, or local discard and destruction if appropriate. Where local discard and destruction is appropriate, the investigator is responsible for ensuring that a local discard/destruction procedure is documented.

9.6 Standard Policies

Trial site personnel will have access to a central electronic treatment allocation/randomization system (IVRS/IWRS system) to allocate subjects, to assign vaccine to subjects and to manage the distribution of clinical supplies. Each person accessing the IVRS system must be assigned an individual unique PIN. They must use only their assigned PIN to access the system, and they must not share their assigned PIN with anyone.

10.0 ADMINISTRATIVE AND REGULATORY DETAILS

10.1 Confidentiality

10.1.1 Confidentiality of Data

By signing this protocol, the investigator affirms to the Sponsor that information furnished to the investigator by the Sponsor will be maintained in confidence, and such information will be divulged to the institutional review board, ethics review committee (IRB/ERC) or similar or expert committee; affiliated institution and employees, only under an appropriate understanding of confidentiality with such board or committee, affiliated institution and employees. Data generated by this trial will be considered confidential by the investigator, except to the extent that it is included in a publication as provided in the Publications section of this protocol.

